### 4.1.5 MEAN CHANGE IN TOTAL MEIBOMIAN GLAND SCORE FROM BASELINE TO 1 MONTH POSTOPERATIVE

The total Meibomian gland score is the sum of the grades for all 15 glands with a range of 0 to 45. Total Meibomian gland score will be presented by study group eyes and

Version 1.0 3 SAP/DRYE-102-SELF

control group eyes. Change in total Meibomian gland score is defined as total Meibomian gland score at 1 month postoperative visit minus the score at Baseline (before the LipiFlow treatment). A higher total Meibomian gland score reflects better Meibomian gland function. Greater mean change in total Meibomian gland score is expected for study group eyes than that for control group eyes. The right eyes and left eyes data from each group will also be presented.

#### 4.2 OTHER ENDPOINTS

#### 4.2.1 ENDPOINTS EVALUATED AT 1-MONTH POSTOPERATIVELY

Mean change in number of Meibomian Gland Yielding Liquid Secretion (MGYLS) from Baseline visit will be compared between study group eyes and control group eyes. The number of MGYLS (i.e., cloudy or clear liquid with a grade of 2 or 3) will be counted out of the 15 glands assessed with a range of 0 to 15. Mean number of MGYLS will be reported at Baseline visit and 1 month postoperatively. A higher number of MGYLS indicates better Meibomian gland function. Change in number of MGYLS is defined as number of MGYLS at 1 month visit minus number of MGYLS at Baseline visit. Mean change in number of MGYLS from baseline to 1 month postoperative visit is expected to be greater for study group eyes than that for control group eyes.

Mean change in ocular surface stain grade from Baseline visit will be compared between study group eyes and control group eyes. Corneal staining will be evaluated in five corneal regions on a scale of 0 (none), 1 (mild), 2 (moderate) and 3 (severe). The total corneal staining grade will be calculated as the sum of the grades for each of the five corneal regions on a scale from 0 to 15. A lower grade indicates less corneal surface desiccation. Conjunctival staining will be evaluated in six conjunctival regions on a scale of 0 (none), 1 (mild), 2 (moderate) and 3 (severe). The total conjunctival staining grade will be calculated as the sum of the grades for each of the six conjunctival regions on a scale from 0 to 18. A lower grade indicates less conjunctival surface desiccation. Mean ocular surface stain grade score will be reported at Baseline visit and 1 month postoperatively. Change in ocular surface stain grade score is defined as the score at 1 month visit minus the score at Baseline visit.

Mean change in Tear Break-up Time (TBUT) from Baseline will be compared between study group eyes and control group eyes. Three separate measurements of TBUT will be taken on each eye and the average of the three measurements will be calculated for analysis. Mean TBUT will be reported at Baseline visit and 1 month postoperatively. Change in TBUT is defined as TBUT at 1 month visit minus TBUT at Baseline visit. A higher tear break-up time indicates greater tear film stability. Mean change in TBUT from baseline to 1 month postoperative is expected to be greater for study group eyes than that for control group eyes.

Version 1.0 4 SAP/DRYE-102-SELF

Change in Eyelid Margin Evaluation from Baseline visit will be compared between study group eyes and control group eyes. The eyelid appearance will be graded as 'Obvious lid changes', 'Minimal lid changes' or 'Normal lid appearance'. In addition, the eyelids for the presence of MGD will be graded as either 'Obvious MGD' or 'Non-obvious MGD'. The frequency and percent of eyelid assessment and MGD presence assessment will be presented at Baseline visit and 1 month postoperatively.

#### 4.2.2 ENDPOINTS EVALUATED AT 3-MONTH POSTOPERATIVELY

Mean LogMAR monocular BCDVA, mean LogMAR binocular UCDVA, UCIVA, UCNVA, BCDVA and contrast acuity will be reported for study group eyes/subjects and control group eyes/subjects at 3 months postoperatively. Better visual acuity outcomes (lower mean LogMAR scores) for study group eyes are expected compared to control group eyes.

Summary statistics (mean, standard deviation, median, minimum and maximum) will be reported for MRSE at 3 months postoperative visit for study group eyes and control group eyes. The difference between MRSE at 3 months postoperative visit and the target MRSE will be calculated. The difference is expected to be smaller (closer to zero) for study group eyes than that for control group eyes.

Mean change in total Standard Patient Evaluation of Eye Dryness (SPEED) score from Baseline visit to 3 months postoperative in the study group subjects will be compared to the control group subjects. The SPEED score is the sum of frequency and severity scores with a range from 0 to 28. A lower SPEED score represents less frequent and/or less severe dry eye symptoms. The mean SPEED score will be reported at Baseline and 3 months postoperative visit. Greater mean change in SPEED score from Baseline to 3 months for study group subjects is expected.

Mean change in total Meibomian gland score from Baseline visit in the study group eyes will be compared to the control group eyes. Greater mean change in total Meibomian gland score is expected for study group eyes than that for control group eyes.

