6.2 OTHER ENDPOINTS

- 1-Month Postoperative Visit:
 - Mean change in Number of Meibomian Glands Yielding Liquid Secretion (MGYLS) from Baseline visit to 1 month postoperative in the Study group compared to the Control group.
 - Mean change in ocular surface stain grade from Baseline visit to 1 month postoperative in the Study group compared to the Control group.
 - Mean change in Tear Break-up Time (TBUT) from Baseline visit to 1 month postoperative in the Study group compared to the Control group.
 - Mean change in Eyelid Margin Evaluation from Baseline visit to 1 month postoperative in the Study group compared to the Control group.
- 3-Month Postoperative Visit:
 - Mean monocular BCDVA in the Study group at 3 months postoperative compared to the Control group.
 - Mean binocular UCDVA and BCDVA in the Study group at 3 months postoperative compared to the Control group.
 - Mean binocular UCIVA in the Study group at 3 months postoperative compared to the control.
 - Mean binocular UCNVA in the Study group at 3 months postoperative compared to the Control group.
 - Mean manifest refraction spherical equivalent (MRSE) at 3 months postoperative compared to target MRSE in the Study group compared to the Control group.
 - Contrast acuity in the Study group at 3 months postoperative compared to the Control group.
 - Mean change in total Standard Patient Evaluation of Eye Dryness (SPEED) score from Baseline visit to 3 months postoperative in the Study group compared to the Control group.
 - Mean change in total meibomian gland score in the Study group compared to the Control group from Baseline to 3 months postoperative.

- Control Group 4-Months Postoperative Visit:
 - Mean change in monocular UCDVA and BCDVA from 3 months to 4 months postoperative.
 - Mean change in binocular UCDVA and BCDVA from 3 months to 4 months postoperative
 - Mean change in binocular UCIVA from 3 months to 4 months postoperative
 - Mean change in binocular UCNVA from 3 months to 4 months postoperative
 - Mean MRSE at 4 months postoperative compared to target MRSE
 - Percent of eyes with MRSE within 0.50 D and within 1.00 D of target MRSE at 4 months postoperative
 - Contrast acuity at 4 months postoperative compared to 3-month.
 - Mean change in total meibomian gland score from 3 months to 4 months postoperative.
 - Mean change in total SPEED score from 3 months to 4 months postoperative.
- Rate of adverse events in the Study and Control groups.

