- Change in Eyelid Margin Evaluation from Baseline visit to 1 month postoperative in the Study group compared to the Control group.

The eyelid appearance will be graded as 'Obvious lid changes', 'Minimal lid changes' or 'Normal lid changes'. In addition, the eyelids for the presence of MGD will be graded as either 'Obvious MGD' or 'Non-obvious MGD'. The frequency and percent of eyelid assessment and MGD presence assessment will be presented at Baseline visit and 1 month postoperatively.

- **3-Month Postoperative Visit:**

- Mean LogMAR monocular BCDVA, mean binocular UCDVA, UCIVA, UCNVA, BCDVA, and contrast acuity will be reported for study group eyes and control group eyes at 3 months postoperative. Better visual acuity outcomes (lower mean LogMAR scores) for study group eyes are expected compared to control group eyes. Summary statistics (mean, standard deviation, median, minimum and maximum) will be reported for MRSE at 3 months postoperative for study group eyes and control group eyes. The difference between MRSE at 3 months postoperative visit and the target MRSE will be calculated. The difference is expected to be smaller (closer to zero) for study group eyes than that for control group eyes. Contrast acuity in the Study group at 3 months postoperative will be compared to the Control group.
- Mean change in total Standard Patient Evaluation of Eye Dryness (SPEED) score from Baseline visit to 3 months postoperative in the Study group will be compared to the Control group.

The SPEED score is the sum of frequency and severity scores with a range from 0 to 28. A lower SPEED score represents less frequent and/or less severe symptoms. The mean SPEED score will be reported at Baseline and 3 months postoperative visit. Greater mean change in SPEED score from Baseline to 3 months for study group eyes is expected.

- Mean change in total meibomian gland score in the Study group will be compared to the Control group from Baseline to 3 months postoperative. Greater mean change in total Meibomian gland score from Baseline to 3 months is expected for study group eyes than that for control group eyes.

- **Control Group 4-Month Postoperative Visit:**

- Mean change in LogMAR monocular BCDVA and UCDVA and mean change in LogMAR binocular UCDVA, UCIVA, UCNVA, BCDVA, and contrast acuity will be reported for control group eyes from 3 months to 4 months postoperative. Better visual acuity outcomes (lower mean LogMAR scores) at 4 months visit are expected.

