#### 4.1.3 RATE OF REFRACTIVE PREDICTABILITY AT 3 MONTHS POSTOPERATIVE

The achieved MRSE is defined as "Postop MRSE – Targeted MRSE". The frequency, proportion and 95% confidence intervals of eyes with achieved MRSE within 0.50 D and 1.00 D of targeted MRSE will be summarized at 3 months postoperatively. The proportion of study group eyes with achieved MRSE within 0.50D and within 1.00D of targeted MRSE is expected to be greater compared to control group eyes. The right eyes and left eyes data from each group will also be presented.

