### 4.2.3 ENDPOINTS EVALUATED AT 4-MONTH POSTOPERATIVE FOR CONTROL GROUP SUBJECTS ONLY

Mean change in LogMAR monocular BCDVA and UCDVA and mean change in LogMAR binocular UCDVA, UCIVA, UCNVA, BCDVA and contrast acuity will be reported for control group eyes from 3 months to 4 months postoperative visit. Better visual acuity outcomes (lower mean LogMAR scores) at 4 months visit are expected.

Mean MRSE at 4 months postoperative will be compared to target MRSE. Frequency and percent of eyes with MRSE within 0.50 D and within 1.00 D of target MRSE at 4 months postoperative will be reported.

Version 1.0 5 SAP/DRYE-102-SELF

Mean change in total Meibomian gland score and mean change in total SPEED score from 3 months to 4 months postoperative will be reported. An increase in both mean total Meibomian gland score and mean total SPEED are expected.

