Mean monocular BCDVA - (N, Mean, SD, Min, Max, 95% Cl of LogMAR)  Monocular BCDVA by acuity line over time (n and % within each category)	х	eyes
Mean binocular UCDVA, UCIVA, UCNVA, BCDVA - (N, Mean, SD, Min, Max, 95% CI of LogMAR) Binocular UCDVA, UCIVA, UCNVA, BCDVA by acuity line over time (n and % within each category)	х	Subjects
MRSE at 3M - (N, Mean, SD, Min, Max, 95% CI)  Difference between 3M MRSE and target MRSE - (N, Mean, SD, Min, Max, 95% CI)	х	eyes
Contrast acuity at 3M - (N, Mean, SD, Min, Max, 95% CI of LogMAR)	х	Subjects
Mean change in SPEED score from baseline- (N, Mean, SD, Min, Max, 95% CI)	х	eyes
Mean change in total Meibomian gland score from baseline- (N, Mean, SD, Min, Max, 95% CI)	х	eyes

ENDPOINTS EVALUATED at 4-MONTH POSTOP		
Mean monocular BCDVA and UCDVA and change from 3M to 4M - (N, Mean, SD, Min, Max, 95% Cl of LogMAR)	х	Control group eyes only
Monocular BCDVA and UCDVA by acuity line over time (n and % within each category)		
Mean binocular UCDVA, UCIVA, UCNVA, BCDVA and change from 3M to 4M - (N, Mean, SD, Min, Max, 95% CI of LogMAR) Binocular UCDVA, UCIVA, UCNVA, BCDVA by acuity line over time (n and % within each category)	х	Control group subjects only
MRSE at 4M - (N, Mean, SD, Min, Max, 95% CI)  Difference between 4M MRSE and target MRSE - (N, Mean, SD, Min, Max, 95% CI)	х	Control group eyes only
Contrast acuity at 4M and change from 3M to 4M - (N, Mean, SD, Min, Max, 95% CI of LogMAR)	х	Control group subjects only
Mean change in SPEED score from baseline- (N, Mean, SD, Min, Max, 95% CI)	х	Control group eyes only
Mean change in total Meibomian gland score from baseline- (N, Mean, SD, Min, Max, 95% CI)	х	Control group eyes only
RATE OF ADVERSE EVENTS/MEDICAL/LENS FINDINGS		
Type and rate of AE, medical and/or lens findings (n and %)	х	eyes

**KEY**: MGYLS=Meibomian gland yielding liquid secretion, TBUT=tear break-up time, SPEED=standard patient evaluation of eye dryness, MGD=Meibomian gland dysfunction, AC=axial length, ACD=anterior chamber depth, K=keratometric measurements, UCIVA=uncorrected intermediate VA at 66cm, UCNVA=uncorrected near VA at 40cm, UCDVA=uncorrected distance visual acuity, BCDVA=best-corrected distance visual acuity

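### At 3 months the only continuous refractive accuracy summary is a signed error, whose mean measures bias; the absolute error should be added and should carry the stated expectation

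*SAP*

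**What the plan says.** Protocol 6.2 lists among the other endpoints: "Mean manifest refraction spherical equivalent (MRSE) at 3 months postoperative compared to target MRSE in the Study group compared to the Control group". Protocol 20.3 and SAP 4.2.2 put it into practice in the same words: "The difference between MRSE at 3 months postoperative visit and the target MRSE will be calculated". Both then give the expected direction: "The difference is expected to be smaller (closer to zero) for study group eyes than that for control group eyes".

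SAP Appendix I has a 3-month row headed "Difference between 3M MRSE and target MRSE", by group, with N, mean, SD, minimum, maximum and a 95% confidence interval. SAP 4.1.3 takes the refractive error as postoperative minus targeted, so it carries a sign. Neither document defines an absolute difference, or a mean or median absolute error. No test, alpha or success criterion is attached to this endpoint.

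Refractive accuracy is also covered by a key endpoint (Protocol 20.2, SAP 4.1.3): the proportion of eyes within 0.50 D and within 1.00 D of target at 3 months, with 95% confidence intervals.

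**The concern.** Protocol section 3 says that LipiFlow will make the biometry more precise and the refraction more predictable. Protocol 6.1 and SAP 4.1.2 define precision as a standard deviation. If random error in the measurements falls, eyes cluster more tightly around target; the centre of the distribution need not shift. Protocol 10.3 aims every eye at emmetropia, refers to personalised lens constants, and lets surgeons adjust the target in the light of the first eye. All three tend to keep the centre near zero in both arms.

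A signed mean that lies closer to zero therefore shows less bias, not better accuracy. An arm with one eye at +1.00 D and one at -1.00 D has a signed mean of 0. An arm with every eye at -0.25 D has a signed mean of -0.25 D and looks worse, although its mean absolute error is 0.25 D against 1.00 D.

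What is at stake is how one secondary result is read. A gain in accuracy could be reported as no difference, or a chance difference in bias as a gain, in the only continuous measure of distance from target.

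**Working it through.** **Inputs.** The 55 per arm is from SAP section 5, where it serves the UCDVA sizing. That calculation reproduces: 1/(1.6 × √(2/55)) = 3.28, and Φ(3.28 − 1.645) = 95%, in line with the SAP's statement of over 90%. The plan states no figure for the MRSE endpoint and no SD for refractive error, so SDs are assumed. Further assumptions: normal errors, one eye per subject, zero bias in both arms.

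**Signed mean.** Its expectation is 0 in each arm whatever the SD. A two-sided 5% test of the two means therefore rejects about 5% of the time (simulated 4.9 to 5.1%). With no test planned, the expectation might be judged simply by which mean lies nearer zero. For SDs of 0.35 and 0.50 D, the chance that this is the Study arm is (2/π) × arctan(0.50/0.35) = 61%. A coin toss gives 50%.

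**Absolute error.** For SD s, the mean of |error| is s√(2/π) and its SD is s√(1 − 2/π).
- Study (0.35): mean 0.279, SD 0.211
- Control (0.50): mean 0.399, SD 0.301
- Difference: 0.120; standard error √((0.211² + 0.301²)/55) = 0.0496; ratio 2.41
- One-sided 5% power: Φ(2.41 − 1.645) = 78%, and 78 to 79% by simulation

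The two-sided figure, like for like with the 5% above, is 67 to 68%.

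**Within 0.50 D.** The rate is 2Φ(0.50/s) − 1: 84.7% for Study and 68.3% for Control. The pooled rate is 76.5%, so the null standard error is √(2 × 0.765 × 0.235/55) = 0.081. The standard error under the alternative is √((0.847 × 0.153 + 0.683 × 0.317)/55) = 0.079. One-sided power is Φ((0.164 − 1.645 × 0.081)/0.079) = 65%, and 65 to 66% by simulation.

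| SD Study / Control (D) | Signed mean, two-sided rejection | Mean absolute error, Study / Control (D) | Absolute error, one-sided power | Within 0.50 D, Study / Control | Rate, one-sided power |
|---|---|---|---|---|---|
| 0.35 / 0.50 | 5% | 0.28 / 0.40 | 78–79% | 84.7% / 68.3% | 65–66% |
| 0.375 / 0.50 | 5% | 0.30 / 0.40 | 62% | 81.8% / 68.3% | 50% |
| 0.40 / 0.50 | 5% | 0.32 / 0.40 | 45–46% | 78.9% / 68.3% | 35–36% |
| 0.40 / 0.60 | 5% | 0.32 / 0.48 | 86% | 78.9% / 59.5% | 71–72% |

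The plan tests none of these quantities. The power figures only rank how informative each summary is.

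**The case against.** **The spread is already reported.** Appendix I lists the SD, minimum and maximum of the same difference, so a tighter Study arm would be visible. Under normality the SD is no weaker than the absolute error: a one-sided variance-ratio test at 0.375 against 0.50 D would have about 67% power, against 62%. This stands. A reader might infer that a gain in accuracy cannot appear in this endpoint at all; that is true of the mean only. But the written expectation concerns the difference, not its SD, and no comparison of SDs is planned.

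**Accuracy regardless of sign is a key endpoint.** The within-0.50 D and within-1.00 D rates answer the study question, and biometric precision is measured directly as well. This stands too. The affected item is an other endpoint without a test. What remains is the loss of information from dichotomising.

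**Closer to zero may mean each eye's distance from zero.** The sentence allows that reading. Yet no absolute value is defined, the endpoint in Protocol 6.2 is named as a mean, and the table row summarises the plain difference. At the least, the wording needs settling.

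**The signed mean is not useless.** If LipiFlow removed a systematic error, the signed mean would show it, and the documents do not demonstrate zero bias. That is a reason to keep it.

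**A reversal is unlikely.** It is tempting to say that the signed mean would favour the less accurate arm. With a -0.10 D offset in the Study arm only (SD 0.35 against 0.50 D), the Study mean is nearer zero in about 22% of simulated trials. Nothing in the documents suggests a one-arm offset, and randomisation is stratified by site, so offsets from surgeons or lens constants should be shared. With a common -0.10 D offset the figure is about 51%.

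**Conclusion.** The point holds for the 3-month endpoint as a worthwhile refinement. The mean that carries the stated expectation measures bias, while the hypothesis concerns spread. Under the assumed SDs the signed mean has no power beyond its alpha. Mean absolute error would have about 45 to 86% one-sided power and the within-0.50 D rate about 35 to 72%, an advantage of roughly 10 to 14 percentage points. These figures rest on assumed SDs of 0.35 to 0.40 D (Study) and 0.50 to 0.60 D (Control), normal errors, no bias and one eye per subject. The trial's accuracy question is not lost, and no key endpoint is affected.

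A reader might extend the point to 4 months, where the SAP says: "Mean MRSE at 4 months postoperative will be compared to target MRSE". The documents do not support that. SAP 4.2.3 covers control eyes only and states no between-group expectation for refraction. The crossover LipiFlow treatment comes after the 3-month visit, hence after biometry, lens choice and implantation, so better biometry cannot act there. The within-0.50 D and within-1.00 D rates are reported at that visit as well.

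**What to change.** In SAP 4.2.2 and Protocol 20.3, define for each eye the absolute difference |3-month MRSE − target MRSE|. Report its mean and median by group, with SD and 95% confidence interval, and state that this quantity is expected to be smaller in the Study group. Keep the signed mean and its SD, labelled as descriptions of bias and spread. Add one row to the 3-month block of SAP Appendix I, and align the endpoint wording in Protocol 6.2 and the synopsis. Leave SAP 4.2.3 as it is.

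The cost is one derived variable, one table row and a reworded sentence in each document. No new data, visits or subjects are needed. The change should be made before the 3-month refractive data are analysed.

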### 4.2.3 ENDPOINTS EVALUATED AT 4-MONTH POSTOPERATIVE FOR CONTROL GROUP SUBJECTS ONLY

Mean change in LogMAR monocular BCDVA and UCDVA and mean change in LogMAR binocular UCDVA, UCIVA, UCNVA, BCDVA and contrast acuity will be reported for control group eyes from 3 months to 4 months postoperative visit. Better visual acuity outcomes (lower mean LogMAR scores) at 4 months visit are expected.

Mean MRSE at 4 months postoperative will be compared to target MRSE. Frequency and percent of eyes with MRSE within 0.50 D and within 1.00 D of target MRSE at 4 months postoperative will be reported.

Version 1.0 5 SAP/DRYE-102-SELF

Mean change in total Meibomian gland score and mean change in total SPEED score from 3 months to 4 months postoperative will be reported. An increase in both mean total Meibomian gland score and mean total SPEED are expected.

#### 4.2.4 RATE OF ADVERSE EVENTS/MEDICAL AND/OR LENS FINDINGS

The frequency and proportion of eyes with optical/visual, medical and lens complications will be reported over time. The type and rates of adverse events will be summarized for both study group eyes and control group eyes.

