4. STUDY DESIGN

This study is a 6-month, post-market, prospective, randomized, multicenter, bilateral, open-label, cross-over, comparative clinical investigation.

The study will be conducted at up to 7 sites in the U.S.A. Approximately 140 subjects will be randomized and bilaterally implanted, to achieve approximately 110 evaluable subjects (55 in the study arm and 55 in the control arm). Subjects are to be treated on both eyes by LipiFlow and to be implanted bilaterally with the Symphony IOLs.

JUSTIFICATION OF STUDY DESIGN

The study is to be conducted in USA as a post-market study. The study is designed to evaluate improvements in biometry reliability, visual outcomes and refractive outcomes after LipiFlow treatment versus an active control group and, through a cross-over design, to evaluate visual and refractive outcomes after postoperative LipiFlow treatment. The study design allows evaluation of preoperative and postoperative LipiFlow treatments on cataract surgery outcomes.

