11. ADVERSE EVENTS AND PRODUCT COMPLAINTS

11.1 ADVERSE EVENT DEFINITIONS

Adverse Event (AE)

An adverse event is defined (following ISO 14155) as any untoward medical occurrence, unintended disease or injury, or untoward clinical signs (including abnormal laboratory findings) in subjects, users or other persons, whether or not related to the study device.

Serious Adverse Event (SAE)

An adverse event is considered serious (following ISO 14155) if it is an untoward occurrence which may or may not be related to use of the study device that

- is sight- or life-threatening,
- results in death,
- requires inpatient hospitalization or prolongation of hospitalization (a planned hospitalization for a pre-existing condition without a serious deterioration in health is not considered a serious adverse event),

- results in permanent impairment of a body structure or body function,
- necessitates medical or surgical intervention to prevent permanent impairment to a body structure or function, or
- results in fetal distress, fetal death or a congenital abnormality or birth defect

Device-Related Adverse Event/Adverse Device Effect (ADE)

A device-related adverse event is defined as any adverse even that is believed to be definitely, probably or possibly related to the study device (following the guidelines in Section 11.4, Causal Relationship). A device-related event is also considered an adverse device effect (ADE; following ISO 14155) resulting from the use of the study device that may result from user error, insufficiencies or inadequacies in the instructions for use, deployment, implantation, installation, operation of any malfunction of the device.

Study-Specific Serious Anticipated Adverse Events

The following is a list including, but not limited to, ocular serious adverse events that are anticipated and must be reported to JJSV for this study. Adverse event definitions in accordance with the American Academy of Ophthalmology Task Force Consensus Statement are included in **Appendix U**.

- Endophthalmitis/Intraocular infection
- Hypopyon
- Hyphema
- IOL dislocation
- Cystoid macular edema
- Pupillary block
- Retinal detachment/tear
- Persistent corneal edema
- Persistent iritis
- Persistent uveitis
- Persistent raised IOP requiring treatment
- Toxic anterior segment syndrome
- Visual symptoms requiring secondary surgical intervention (e.g., lens removal)
- Tilt and decentration requiring secondary surgical intervention (e.g., repositioning)

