11.3 ADVERSE EVENT AND COMPLAINT REPORTING REQUIREMENTS

All adverse events and any complaint encountered using any JJSV product, regardless of severity and whether or not attributed to the study device(s), are to be reported to JJSV and recorded on the case report form corresponding to the visit during which awareness of the event occurred. Adverse events are also to be reported to the reviewing IRB as per the IRB's reporting requirements. If required, adverse events will be reported to the appropriate regulatory agencies (e.g., FDA) according to all applicable laws and regulations.

Reporting of adverse events shall follow the USA Code of Federal Regulations for sites in the USA. General guidelines are provided below:

Adverse Event Reporting

An adverse event that is not serious or device-related is to be reported to JJSV in a timely manner. Notification of non-serious and non-device related adverse events will occur by recording events on the CRF when noted. Such adverse events are also to be reported to the reviewing IRB per their reporting requirements.

Complaints/Device Deficiency Reporting

A general product complaint or device deficiency is to be reported to JJSV in a timely manner. Notification of complaints/device deficiencies will occur by either recording complaints on the CRF when the complaint occurred (e.g. operative form) or by a phone call to the Sponsor. Any device deficiency that could have led to a serious adverse event without suitable action or intervention, or under less fortunate circumstances, must be reported to the sponsor immediately (no later than 48 hours after detection). Device deficiencies that could have led to a serious adverse event should also be reported to the investigator's IRB per their reporting requirements.

Serious and/or Device-Related Adverse Event Reporting

Serious and/or device related events (ADEs) are to be documented using the Serious Adverse Event/Adverse Device Effect (SAE/ADE) CRF. In the event of a serious adverse event (SAE), which may or may not be related to use of the study device, JJSV must be notified immediately (no later than 48 hours after detection). Any SAE is to be reported by phone (and/or email) and by submitting the completed SAE/ADE CRF. Any SAE or device-related AE should also be reported to the investigator's IRB per their reporting requirements.

Unanticipated Adverse Device Effect (UADE)/Unanticipated Serious Adverse Device Effect (USADE) Reporting

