- Mean MRSE at 4 months postoperative will be compared to target MRSE.
- Frequency and percent of eyes with MRSE within 0.50 D and within 1.00 D of target MRSE at 4 months postoperative will be reported.
- Mean change in total meibomian gland score and mean change in total SPEED score from 3 months to 4 months postoperative will be reported. An increase in both total Meibomian gland score and total SPEED are expected.
- The frequency and proportion of eyes with optical/visual, medical and lens complications will also be reported over time. Rate of adverse events will be reported in the Study and Control groups.

[figure not shown]

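### Adverse events are to be summarized per eye only, a unit that does not fit non-ocular events and gives no per-patient risk for a bilateral treatment

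*SAP*

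**What the plan says.** SAP 4.2.4 fixes the unit: "The type and rates of adverse events will be summarized for both study group eyes and control group eyes". In SAP Appendix I, one row covers adverse events together with medical and lens findings, and its note column reads eyes, with no entry for subjects. Neither document plans a count or percentage of subjects with at least one adverse event, or gives a rule for an event that belongs to neither eye.

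The protocol is wider in scope and silent on the unit.

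- Section 11.1 defines an adverse event as "any untoward medical occurrence, unintended disease or injury, or untoward clinical signs", whether or not device-related. Its criteria for a serious event include death and an event that "requires inpatient hospitalization or prolongation of hospitalization".
- Section 11.3 requires that all such events, "regardless of severity and whether or not attributed to the study device(s), are to be reported to JJSV".
- Section 20.3 reports optical/visual, medical and lens complications by eye, and then says only: "Rate of adverse events will be reported in the Study and Control groups".
- Section 4 makes the treatment bilateral: "Subjects are to be treated on both eyes by LipiFlow and to be implanted bilaterally".

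SAP 2.1 sets the population for everything except biometric precision as eyes randomized and implanted.

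**The concern.** The SAP assigns a unit to each output. Demographics, binocular acuity and bothersome symptoms are by subject, and accountability is by subject and by eye. Adverse events are by eye alone. That unit suits a lens finding or an eyelid reaction. It does not suit a hospitalization or a death, which the protocol also collects. Whoever programs the table must choose among several treatments of such events, in an open-label trial and after the data exist.

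For ocular events the per-eye rate is a legitimate quantity, but it does not answer the question a patient or physician would ask. A patient accepts LipiFlow and surgery in both eyes, and wants to know the chance of at least one event. The plan never produces that number. At stake is how the safety results can be read and used, since the rate of adverse events in the two groups is a listed endpoint (Protocol 6.2).

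**Working it through.** The documents give no adverse event rate, so there is no planned figure to reproduce. The check asks what the stated unit does to each kind of event.

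**Inputs**

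- Evaluable subjects per arm: 55 (SAP 1 and 5), hence 2 × 55 = 110 eyes if both eyes of every subject are counted.
- Eyes treated per subject: 2 (Protocol 4).
- Between-eye correlation: SAP 2.1 expects it to be positive but gives no value. I assume a range of 0 to 1, plus the extreme in which every event is in one eye only.
- Event counts and per-eye event rates: assumed for illustration.

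**Non-ocular events.** Suppose 3 of 55 subjects in an arm have one.

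| Handling | Result |
|---|---|
| Per subject | 3/55 = 5.5% |
| Per eye, entered once | 3/110 = 2.7% |
| Per eye, assigned to both eyes | 6/110 = 5.5% |
| Left out of the eye table | not shown |

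Assigning the event to both eyes reproduces the correct percentage but doubles the count. Entering it once halves the percentage. The SAP does not choose.

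**Ocular events, by counting.** Suppose 6 of 55 subjects are affected, so 6/55 = 10.9% of subjects.

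- All unilateral: 6/110 = 5.5% of eyes, ratio of per-eye to per-subject 0.50.
- Three of the six bilateral: (6 + 3)/110 = 8.2% of eyes, ratio 0.75.
- All bilateral: 12/110 = 10.9% of eyes, ratio 1.00.

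**Ocular events, by probability.** Let p be the per-eye event probability and φ the between-eye correlation. The probability that both eyes are affected is p² + φp(1 − p), so

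per-subject risk = 2p − [p² + φp(1 − p)].

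At p = 0.05, p² = 0.0025 and p(1 − p) = 0.0475:

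| Case | Per-subject risk | Per-eye ÷ per-subject |
|---|---|---|
| All unilateral | 0.10 = 10.0% | 0.50 |
| φ = 0 | 0.10 − 0.0025 = 9.75% | 0.51 |
| φ = 0.25 | 0.10 − 0.0144 = 8.6% | 0.58 |
| φ = 0.5 | 0.10 − 0.0263 = 7.4% | 0.68 |
| φ = 0.75 | 0.10 − 0.0381 = 6.2% | 0.81 |
| φ = 1 | 0.10 − 0.05 = 5.0% | 1.00 |

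The ratio depends little on p: for p from 1% to 20% it is 0.50 to 0.56 at φ = 0 and 0.67 to 0.71 at φ = 0.5.

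**Follow-up and population.** Protocol 10.2 gives Control subjects LipiFlow 0 to 7 days after the 3-month visit and sees them again 4 to 6 weeks after that, so their follow-up runs roughly 4 to 7 weeks beyond the Study group's last visit. A by-arm table over all follow-up would therefore mix Control time before and after LipiFlow. Separately, Protocol 10.7 foresees randomized subjects who never receive a study lens. A Study subject who had LipiFlow and was never implanted falls outside the population of SAP 2.1, and so would any event in that subject.

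**The case against.** The best defence is that eye-level reporting suits this trial. The LipiFlow risks listed in Protocol 17 are all events of the eye or eyelid, and the serious events named in Protocol 11.1 are ocular, although that list is expressly not exhaustive. This justifies keeping a per-eye table. It does not supply a unit for the non-ocular events that the protocol also collects.

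It could also be said that the unit label is a slip. The note column of Appendix I is not fully dependable: it marks change in SPEED score as eyes, although SAP 4.2.2 compares subjects. For adverse events, however, the text and the table agree on eyes.

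Several stronger readings are tempting, and the documents do not support them.

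- *There is no valid denominator for non-ocular events.* SAP 3.1 and the accountability rows of Appendix I already give subject counts by arm. What is missing is an adverse event output that uses them.
- *Per-eye rates always understate patient risk, by half.* Half is the limit when every event is unilateral. With the positive correlation that SAP 2.1 expects, the shortfall is smaller, and it vanishes if all events are bilateral.
- *An event copied to both eyes inflates the rate.* It doubles the count only, because the denominator doubles as well (6/110 = 3/55).
- *The comparison of arms is biased.* If the share of bilateral events is similar in the two arms, the conversion from eyes to subjects is similar too. Nothing in the documents suggests otherwise, and no test or success criterion is attached to adverse events.
- *Serious non-ocular events escape oversight.* Protocol 11.3 requires a dedicated form and notification within 48 hours for serious events, and Protocol 15.3 has the medical monitor review them.

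**Conclusion.** The point holds as a gap in the reported safety results. The only unit the SAP states for adverse events does not fit the non-ocular ones, and no per-patient risk is planned for a treatment given to both eyes.

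In the illustration, a non-ocular event in 3 of 55 subjects could appear as 2.7%, as 5.5% with a doubled count, or not at all. For ocular events the per-eye percentage is 0.5 to 1.0 times the per-subject percentage, and where it falls depends on a between-eye correlation that the documents do not give. These figures assume that both eyes of every subject enter the denominator. Subjects implanted in one eye only (Protocol 10.6, Note 3) would shift them slightly. The change should be made before the adverse event tables are produced, but it affects no efficacy result and no safety oversight during the trial.

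**What to change.** In SAP 4.2.4 and Appendix I:

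1. Add the number and percentage of subjects with at least one event, by arm, for: any adverse event, serious, device-related, ocular and non-ocular. Take the denominators from the subject counts already planned.
2. Report non-ocular events per subject only. Keep the per-eye table for ocular events and medical or lens findings.
3. Compare the arms on events through the 3-month visit. Show Control events after crossover LipiFlow in a separate column, without a between-arm comparison.
4. Define the population for these tables as all randomized subjects who received LipiFlow or a study lens, so that events in treated but never-implanted subjects are counted. Because Study subjects can enter this set before surgery and Control subjects cannot, state by arm how many entered without an implant.

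The cost is one extra table and a short population definition, from data already collected. Visits, procedures, sample size and efficacy analyses are unchanged. The sponsor should expect ocular rates per patient that are equal to or higher than the per-eye rates.
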